Appendix 9. Patient Diary

Please indicate at what stage you were able to return to work and your normal daily activities (the activities you were able to do prior to treatment).

Please also indicate the day when you stopped wearing the compression stockings (if provided).

(Please tick one box)

	Day I was able to resume my normal activities	Day I returned to work	Day I stopped wearing compression stockings (if provided)
Day of surgery			
Day after surgery			
2 days after surgery			
3 days after surgery			
4 days after surgery			
5 days after surgery			
6 days after surgery			
7 days after surgery			
8 days after surgery			
9 days after surgery			
10 days after surgery			
>10 days after surgery			

Please return to:

[name]
Academic Department of Vascular Surgery
[name]
Charing Cross Hospital
[name]
London
[name]
[contact]

Appendix 10. Patient Pain Diary (VAS)

Please put a mark on the line to indicate your maximum pain score on each day.

Please also write a score from 0 to 10 for your maximum pain on each day.

Example: *If your pain score on day 4 is roughly about 5 over 10 (10 being the worst pain imaginable), you might want to indicate it as below:*

Day 4	No pain		Worst pain imaginable
--------------	---------	--	--------------------------

Study Diary:

(0 = no pain and 10 = worst pain imaginable)

Day 0	No pain		Worst pain imaginable
Day 1	No pain		Worst pain imaginable
Day 2	No pain		Worst pain imaginable
Day 3	No pain		Worst pain imaginable
Day 4	No pain		Worst pain imaginable
Day 5	No pain		Worst pain imaginable
Day 6	No pain		Worst pain imaginable
Day 7	No pain		Worst pain imaginable
Day 8	No pain		Worst pain imaginable
Day 9	No pain		Worst pain imaginable
Day 10	No pain		Worst pain imaginable

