**Multicentre Randomised Controlled Trial of
Compression Therapy following Endovenous Thermal
Ablation of Varicose Veins**

FULL TITLE

A multicentre randomised controlled trial of compression therapy following endovenous thermal ablation of varicose veins.

SUMMARY

This study will be looking at the effect of compression therapy in patients having endovenous treatment for truncal incompetence of their varicose veins using either radiofrequency ablation (RFA) or endovenous laser therapy (EVLT). Patients will be randomised to either the compression group (group A) or the no compression group (group B).

The pain scores, compliance, quality of life scores, occlusion rate at 6 months as well as the cost effectiveness of each intervention will be assessed.

OBJECTIVES

- Primary Objective

Patient's pain score for the first 10 days post-procedure using the visual analogue scale (VAS)

- Secondary Objective

The secondary objectives would be to compare the two treatment groups with respect to:

- The quality of life scores at baseline, 2 weeks and 6 months using the EQ-5D, AVVQ and CIVIQ scores
- The clinical change using the VCSS at baseline, 2 weeks and 6 months
- The degree of bruising and phlebitis at 2 weeks and 6 months
- The patient compliance with the intervention
- The time taken to return to work and normal activities
- Occlusion rates at 6 months
- Comparison of the cost effectiveness of the intervention

Background

Varicose veins are common and are known to affect approximately one third of the population¹. Chronic venous disease (CVD) has been shown to have a negative impact on the quality of life of patients and treatment of varicose veins has been demonstrated to lead to improvement in the quality of life of patients²⁻⁴. Over the past decade, new endovenous techniques have been introduced and these are felt to be cost-effective, especially, when performed in an outpatient or 'office-based' setting⁵.

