Hamel-Desnos et al. undertook a randomised controlled trial looking at the effect of compression in patients receiving foam sclerotherapy of the saphenous vein¹². They noted that patients with compression had similar pain and quality of life scores to patients not wearing any compression. They concluded that additional use of compression had no impact on the effectiveness of obliteration of veins, satisfaction scores, symptoms and quality of life, and that further controlled trials were needed to answer the question of whether using compression results in any difference to the outcome of varicose vein procedures.

We, therefore, propose to undertake a multicentre randomised study looking at the effect of compression therapy after endovenous thermal ablation.

Description

This will be a multicentre randomised clinical trial looking at the impact of wearing or not wearing compression stocking following endothermal ablation (either endovenous laser treatment (EVLT) or radiofrequency ablation (RFA)) of incompetent truncal veins. **If clinically indicated, patients will receive adjuvant treatment (e.g., concurrent phlebectomies or foam injection).**

Patients will be randomised **to** group A (compression) and group B (no compression). Only the use of compression will be randomised while the decision as to which treatment to use will be at the discretion of the clinical team.

Target Population

Patients referred for treatment of symptomatic varicose veins will be recruited if they are found to have primary great saphenous (GSV) or small saphenous vein (SSV) incompetence on colour duplex scan.

Inclusion Criteria

- Adults over 18 years of age
- Symptomatic GSV or SSV vein reflux **>** 0.5 seconds on colour Duplex
- **Recurrent varicose veins (if suitable for endothermal treatment)**

Exclusion Criteria

- Current DVT

- Arterial disease (ABPI<0.8)
- Vein diameter < 3mm
- Patient who are unwilling to participate
- Inability or unwillingness to complete questionnaires

Intervention

Patients will be randomised to have compression (group A) or no compression (group B). The compression therapy used will be Class II compression stockings. The treatment offered will be endothermal ablation (either endovenous laser treatment (EVLT) or radiofrequency ablation (RFA)) of incompetent truncal veins. Adjuvant treatment to tributaries (e.g., concurrent phlebectomy or foam sclerotherapy) will be carried out, if indicated.

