Patients randomised to group A will be asked to wear compression stockings for 1 week.

Patients randomised to group B and undergoing endothermal ablation only will not be provided with any compression. However, if they receive adjuvant treatment to their tributaries, they will be provided with bandages to wear for 24 hours only, with no further compression afterwards.

At baseline, patients will be asked to fill quality of life questionnaires (EQ-5D, AVVQ and CIVIQ) and will have their clinical scores assessed (CEAP and VCSS). On discharge after their varicose vein intervention, they will then be provided with a diary to record their post-procedural pain every day for 10 days using a validated visual analogue scale (VAS) as well as to record when they return to their normal activities and are back to work. They will also be asked to attend a follow-up in 2 weeks and at 6 months.

Patients' GP will also be sent a letter to inform them of their patient's participation in the study.

Follow-up

Patients will be followed up in the outpatient clinic at 2 weeks and 6 months.

Follow-up at 2 Weeks

At the 2 weeks' follow-up, the diary containing details of the pain scores and how soon patients were able to return to normal activities/work will be collected. In addition, patients will be asked about any bruising or phlebitis they have had in the two weeks after their procedure and how compliant they have been with the compression. They will be examined and the Venous Clinical Severity Score (VCSS) will be recorded. They will also be asked to fill in the EQ-5D, AVVQ and CIVIQ scores.

Follow-up at 6 Months

At the 6 months follow-up, patients will be examined and their VCSS will be recorded. They will also be asked to fill the EQ-5D, AVVQ and the CIVIQ scores. They will have a venous Duplex scan to determine occlusion of the treated vein.

Sample Size and Study Duration

We estimated the sample size needed to observe a difference of at least 10mm in the VAS score, with a standard deviation of 20mm. With power at 90% and 5% significance equivalence, we would need to recruit 174 patients (87 per group).

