Appendix 2: Aberdeen Varicose Vein Questionnaire

[figure not shown]
YOUR VARICOSE VEINS

1. Please draw in your varicose veins in the diagram(s) below:-

Legs viewed
from front

Legs viewed
from back

2. In the last two weeks, for how many days did your varicose veins cause you pain or ache?

(Please tick one box for each leg)

	R Leg	L Leg
None at all		
Between 1 and 5 days		
Between 6 and 10 days		
For more than 10 days		

3. During the last two weeks, on how many days did you take painkilling tablets for your varicose veins?

(Please tick one box for each leg)

	R Leg	L Leg
None at all		
Between 1 and 5 days		
Between 6 and 10 days		
For more than 10 days		

- 4. In the last two weeks, how much ankle swelling have you had?**
(Please tick one box)
- | | | |
|--|--------------------------|--|
| None at all |  | |
| Slight ankle swelling |  | |
| Moderate ankle swelling (eg. causing you to sit with your feet up whenever possible) |  | |
| Severe ankle swelling (eg. causing you difficulty putting on your shoes) |  | |
-
- 5. In the last two weeks, have you worn support stockings or tights?**
(Please tick one box for each leg)
- | | R Leg | L Leg |
|--|--------------------------|--------------------------|
| No |  |  |
| Yes, those I bought myself without a doctor's prescription |  |  |
| Yes, those my doctor prescribed for me which I wear occasionally |  |  |
| Yes, those my doctor prescribed for me which I wear every day |  |  |
-
- 6. In the last two weeks, have you had any itching in association with your varicose veins?**
(Please tick one box for each leg)
- | | R Leg | L Leg |
|-------------------------------|--------------------------|--------------------------|
| No |  |  |

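### The primary pain diary does not tie the daily maximum to the treated leg or the procedure, and no planned analysis uses the pain recorded at baseline

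*Combined protocol and SAP*

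**What the plan says.** The primary objective is the patient's VAS pain score over the first 10 days after the procedure. The Intervention section states the purpose and timing of the diary: "On discharge after their varicose vein intervention, they will then be provided with a diary to record their post-procedural pain".

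The diary page in Appendix 10 has two instructions. The first is "Please put a mark on the line to indicate your maximum pain score on each day". The second is "Please also write a score from 0 to 10 for your maximum pain on each day". Neither mentions a leg, a site or the procedure. Rows run from Day 0 to Day 10.

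Other forms in the same protocol are more specific. Question 2 of the AVVQ (Appendix 2) asks "for how many days did your varicose veins cause you pain or ache", with separate boxes for the right and left leg. Item 1 of the CIVIQ-14 (Appendix 8) asks how severe pain in the ankles or legs has been, on a 1 to 5 scale.

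The Inclusion Criteria require "Symptomatic GSV or SSV vein reflux" above a duration threshold. Bilateral disease is not excluded, and the VCSS form (Appendix 6) has a code for it.

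The baseline list in the Intervention section is EQ-5D, AVVQ, CIVIQ, CEAP and VCSS. It contains no VAS. The documents give no analysis model for the daily scores and no plan to adjust them for baseline pain.

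**The concern.** The protocol intends to measure one thing and the form asks for something wider. Taken literally, the instruction is correctly followed by a patient who marks an aching back, or the other, untreated leg, whenever that is the worst pain of the day.

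A daily maximum has a predictable effect in that situation. The recorded score is the larger of treated-leg pain and other pain, so a low treated-leg score is hidden whenever other pain exceeds it. This happens more often in the arm with less leg pain, which pulls the two arms together. At stake are the size of the estimated effect of compression and the power to detect it.

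The second element is precision. Patients enter with symptoms, so some of the spread in diary scores reflects how much pain each had beforehand. The plan collects that information and does not use it.

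**Working it through.** **1. The plan's own figure.** Inputs from Sample Size and Study Duration: difference 10 mm, SD 20 mm, 90% power, 5% significance, 87 per group, 50% loss.

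- Two-sided superiority: n = 2 × [20 × (1.960 + 1.282) / 10]² = 84.06, so 85 per group (86 by the t-test).
- Two one-sided tests for equivalence, margin 10 mm, true difference 0: n = 2 × [20 × (1.645 + 1.645) / 10]² = 86.6, so 87 per group, an exact match.
- Loss: 174 / (1 − 0.5) = 348.

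The stated figures reproduce, within 3% on the superiority reading.

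**2. Power as planned.** SE = 20 × √(2/87) = 3.032 mm. Power = Φ(10/3.032 − 1.960) = Φ(1.338) = 91%.

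**3. How far a maximum dilutes the difference.** The documents say nothing about how common or severe unrelated pain is, so every input in this step is assumed. Treated-leg pain is N(20, 20) in one arm and N(32, 20) in the other, kept within 0-100, which gives a true difference of 10.8 mm and SD 18.2 mm. Other pain is present in a share p of patients in both arms, is independent of leg pain, and is N(m, 20) kept within 0-100. Recorded score = max(leg pain, other pain). Means and SDs were obtained by numerical integration, and power is at 87 per group.

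| Share p | m = 20 mm | m = 30 mm | m = 40 mm | Power |
|---|---|---|---|---|
| 10% | 3.6% smaller | 5.1% | 6.5% | 94-96% |
| 20% | 7.2% | 10.2% | 13.1% | 89-95% |
| 30% | 10.8% | 15.3% | 19.6% | 82-94% |

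With no other pain, power in this model is 97%, because its effect is slightly larger and its SD smaller than the protocol's. On the protocol's own inputs:

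- 10% dilution: Φ(9/3.032 − 1.960) = 84%.
- 20% dilution: Φ(8/3.032 − 1.960) = 75%.

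**4. Under no true effect.** A second simulation gave both arms the same leg pain (mean 25 mm) and the same background pain. The difference in recorded maxima was zero to within 0.05 mm, so no false effect arises.

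**5. If the result is read as equivalence.** The sample-size sentence uses the word equivalence next to the significance level, so the hypothesis is unclear. With margin 10 mm and true difference 10 mm, the chance of wrongly declaring equivalence at 87 per group is about Φ((10 − d)/3.032 − 1.645), where d is the diluted difference:

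- d = 10 mm: 5%.
- d = 9 mm: 9%.
- d = 8 mm: 16%.

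**6. What baseline adjustment is worth.** With correlation r between the baseline item and diary pain (assumed), the residual SD is 20 × √(1 − r²).

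- r = 0.3: SD 19.08, variance down 9%, power Φ(10/2.893 − 1.960) = 93%.
- r = 0.5: SD 17.32, variance down 25%, power Φ(10/2.626 − 1.960) = 97%.

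**The case against.** The strongest reply is that patients do not read the sentence in isolation. The diary is handed over after a vein procedure, its rows begin at Day 0, and the companion diary in Appendix 9 counts days from surgery and asks about stockings. Many patients will take the question to mean pain from the procedure. This stands as a limit on the size of the problem: the calculation in step 3 lets every affected patient report the larger pain every time, which is the full-misreporting case. It does not remove the point, because the documents do not record what patients are told at handover and the printed question is open.

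A second reply is that power is protected. The target of 350 allows for 50% loss by 6 months, whereas the diary is collected at 2 weeks. If fewer are lost by then, more than 87 per group will supply primary data; at 175 per group, power for a difference diluted to 8 mm is 96%. This also stands for power, but extra patients do not undo dilution of the estimate.

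A third reply is that a comparison of post-procedure scores between randomised arms is valid without a baseline value. That is correct. Adjustment is a gain in precision, not a repair of validity.

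A reader might go further and infer that pre-existing pain cannot be separated out, or that a chance imbalance in it cannot be corrected. The documents do not support this. Pain is recorded at baseline by AVVQ question 2 (by leg), CIVIQ-14 item 1, the EQ-5D pain item and the VCSS pain item. None is on the VAS scale, so they cannot be subtracted from the diary score, but they can serve as covariates. What cannot be identified is unrelated pain during days 0-10.

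**Conclusion.** The point holds as a mismatch between what the diary is meant to record and what its two questions ask, together with unused baseline information. The expected consequence is dilution and added noise. Compression is the randomised factor, so unrelated pain is balanced in expectation, and inferring a spurious difference between arms would be wrong.

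The size is uncertain. Dilution of roughly 4-20% rests wholly on an assumed 10-30% of patients having unrelated pain averaging 20-40 mm and always reporting the larger pain. The precision gain, from about 91% to 93-97% power, rests on an assumed correlation of 0.3-0.5. Nothing here shows that 174, or 348 after allowance for loss, is wrong. Dilution is conservative if the trial tests for a difference, but it favours the conclusion if the result is read as equivalence, which the wording of the sample-size section leaves open. The changes are worth making because they cost almost nothing.

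**What to change.** 1. Reword both questions in Appendix 10, the VAS line and the 0 to 10 score, to ask for the maximum pain that day in the treated leg, or in the worse leg if both were treated. This does not exclude pain that was already present in the treated leg; the second change deals with that.

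2. Pre-specify that the primary comparison is adjusted for a baseline pain item already collected: CIVIQ-14 item 1, or AVVQ question 2 for the treated leg.

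3. Optionally, add one identical VAS line for that leg to the baseline questionnaires, completed before the procedure and before the allocation is known, and use it as the covariate instead.

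The cost is a minor amendment to a paper form, a sentence in the analysis plan and, with the optional line, a few seconds of each patient's time. Diaries completed before the change keep the old wording, and those patients would have only the existing baseline items for adjustment.

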Appendix 11. Trial Flowchart
